#### Inclusion criteria

Participants of this study must meet the following inclusion criteria to be eligible to participate in this study:

1. Physicians that have implanted InductOs in a lumbar interbody spine fusion procedure at least once in the 24 months prior to taking this survey

#### Exclusion criteria

Participants meeting any of the following criteria will not be included in the study:

- 1. Physicians that participated in the testing of this survey, if there are substantial changes made to the survey post-pilot i.e. changes which, in the view of the research team, make the participants contributions invalid or potentially compromising of the study objectives
- 2. Physicians that either themselves work for or have immediate family members who work for Medtronic, third parties involved in this study, or a regulatory agency (EMA, MHRA, HPRA, ANSM, BfARM)

During the initial phone call, screening questions will be asked to determine the eligibility of the physician for participation.

#### 9.3 Variables

Information is collected on three main categories, details are described below. The first category is used to describe the population and includes variables around demographics, type of practice, and level of experience in using InductOs. The second category of variables is aimed at measuring the awareness on the risk of heterotopic ossification, the educational materials and knowledge about safe use of InductOs presented in the educational materials. The third set of variables covers the different sources where information on the key messages in the educational materials could have been obtained. A transcription of the intended survey is included in Annex 3.

## First category:

- Physician specialty
- Practice type/hospital
- Years of practicing physician
- Years InductOs is used

- Last time InductOs was implanted
- Number of patients implanted with InductOs in the past 2 years
- Surgical approaches used
- Amount of rhBMP2 used in lumbar interbody spine fusion in one intervertebral space

## Second category:

- Awareness of common adverse reactions that are associated with InductOs when administering InductOs during lumbar interbody fusion
- Knowledge on safe use of InductOs during pre-implantation, implantation and postimplantation of InductOs

#### *Third category*

- Used sources for guidance on InductOs administration
- Use of educational materials

#### 9.4 Data sources

Data will be collected using a standardized online questionnaire that will be translated into the local languages of the countries where the survey is being conducted. The majority of the questions will evaluate the knowledge of physicians on heterotopic ossification and the measures to reduce the risk of occurrence of heterotopic ossification communicated in the educational materials.

The questionnaire will be pre-tested as described in section 9.1.

## 9.5 Study size

The minimum sample size needed to obtain a proportion with confidence interval with the lower limit above the 80 % minimum awareness was calculated. For this calculation an alfa of 0.05 with a two-sided interval and a distance from proportion to limit of 0.1 was used with the expected proportion of 90 %. This leads to a minimum sample size of 35.

To ensure inclusion of data from the different participating countries, this study aims at collecting responses from physicians covering roughly 10 % of purchasing pharmacies that have received InductOs in the past 2 years in each target country. However, if a greater number of respondents complete the questionnaires for a given target group, these responses will be integrated into the analyses.

The following number of completed surveys are planned per country:

France: 15Germany: 15

- United Kingdom: 15

- Ireland: 10

This brings the total to 55 completed surveys which is above the calculated minimum sample size. Taking into account response rate of roughly 60 % and screening failures an estimated 120 surgeons will be screened for eligibility.

Recruitment rate will be monitored by the researchers; and if it becomes apparent that the there is a risk of the study not meeting the recruitment target then other countries with InductOs sales will be included in the study to widen the pool of potential participants. In the selection of additional countries for recruitment, priority will be given to countries where the existing translated materials are used.

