## 4.8 Study size

The minimum sample size needed to obtain a proportion with confidence interval with the lower limit above the 80 % minimum awareness was calculated. For this calculation an alfa of 0.05 with a two-sided interval and a distance from proportion to limit of 0.1 was used with the expected proportion of 90 %. This leads to a minimum sample size of 35.

To ensure inclusion of data from the different participating countries, this study aims at collecting responses from physicians covering roughly 10 % of purchasing pharmacies that have received InductOs in the past 2 years in each target country. This brings the total to 55 completed surveys which is above the calculated minimum sample size. Taking into account response rate of roughly 60 % and screening failures an estimated 120 surgeons will be screened for eligibility.

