## 9.7 Data analysis

The study population will include all physicians who are screened, are eligible for this study, and completed the questionnaire. All statistical summaries in this study will be descriptive. Frequencies and percentages, with 95 % confidence intervals (CIs) where appropriate, will be presented. Country specific data will be presented. Additional exploratory analyses and sensitivity analyses may be conducted to identify difference between groups of responders.

The primary analysis is aimed at evaluating the proportion of physicians that is aware of the risk of heterotopic ossification and measures described in the educational materials to minimize that risk. A respondent is considered to be aware if they answer 75 % of the questions with regards to heterotopic ossification and the applicable minimization measures correctly. In the questionnaire there are 12 (sub)questions raised on the occurrence of heterotopic ossification and the related risk minimization measures. Hence a surgeon needs to answer 9 of these correct to be considered aware. In Annex 3 the (sub)questions included in the scoring of awareness are marked. The aRMM will be considered effective if 80 % of the respondents are aware of the described risk of heterotopic ossification and the appropriate measures to minimize them. With the targeted 55 respondents, this means 44 or more need to be aware.

The secondary analysis is aimed at identifying the source of physician knowledge. Based on the received data it will be determined to what extent the educational materials are used and are considered an important source of information for the respondents.

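### The minimum of 35 is a correct Wald precision figure, but neither 35 nor the planned 55 assures a lower confidence limit above 80 %

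*Protocol*

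**What the plan says.** Section 9.5 of the protocol gives the aim of the calculation: "The minimum sample size needed to obtain a proportion with confidence interval with the lower limit above the 80 % minimum awareness was calculated". The inputs are "an alfa of 0.05 with a two-sided interval", "a distance from proportion to limit of 0.1 was used", and an awareness of 90 % ("with the expected proportion of 90" %). The result is "This leads to a minimum sample size of 35". Section 4.8 gives the same inputs and result.

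The planned number comes from country coverage: 15 each in France, Germany and the United Kingdom, and 10 in Ireland. It is then set against the calculated figure: "This brings the total to 55 completed surveys which is above the calculated minimum sample size".

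Section 9.7 says of the analysis: "Frequencies and percentages, with 95 % confidence intervals (CIs) where appropriate, will be presented". It names no interval method. The same section calls the risk minimisation measures effective if 80 % of respondents are aware, which it translates into 44 or more of 55. The ENCePP checklist in Annex 2 states that no hypothesis is tested.

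**The concern.** The protocol attaches a specific property to a specific number: with 35 completed surveys the lower confidence limit should lie above 80 %. A half-width formula does not give that. It sets the distance from the estimate to the limit at 0.1, so when the expected value is 90 % the limit falls at about 80 % and sampling variation takes it below about as often as above. The Wald interval is also optimistic for a proportion near 90 % in a sample this small, so other standard intervals do worse.

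At stake is how the reported interval is read. Someone who takes 9.5 at its word would expect 55 surveys to put the lower limit above 80 % with a margin to spare if awareness is as high as assumed. They might then read an interval reaching below 80 % as evidence that awareness fell short of 90 %, when such an interval is quite likely even if awareness is 90 %.

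**Working it through.** **Inputs.** From section 9.5: two-sided alpha 0.05 (z = 1.96), expected proportion p = 0.90, distance d = 0.10, stated minimum 35, planned 55. From section 9.7: effectiveness threshold 44 of 55. Respondents are treated as independent binomial observations.

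**1. The protocol's own figure.** n = z² p(1 − p) / d² = 1.96² × 0.9 × 0.1 / 0.1² = 34.57, rounded up to 35. The figure reproduces.

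**2. What 35 guarantees.** With an observed proportion of exactly 0.90, the Wald lower limit is 0.90 − 1.96 × √(0.9 × 0.1 / 35) = 0.90 − 0.0994 = 0.8006. But 90 % of 35 is 31.5, which cannot be observed. The nearest possible counts give these lower limits:

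| Aware | Observed | Wald | Wilson | Exact |
|---|---|---|---|---|
| 31/35 | 88.6 % | 78.0 % | 74.1 % | 73.3 % |
| 32/35 | 91.4 % | 82.2 % | 77.6 % | 76.9 % |
| 33/35 | 94.3 % | above 80 % | 81.4 % | 80.8 % |

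So the limit clears 80 % from 32 upwards with Wald, and from 33 upwards with Wilson or exact.

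**3. The same for 55.** Plain Wald clears 80 % from 49 upwards (49/55: 80.9 %; 48/55: 78.5 %). Exact clears it from 50 upwards (50/55: 80.05 %; 49/55: 77.8 %), as does Wilson (50/55: 80.4 %; 49/55: 78.2 %).

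**4. Probability of reaching the aim at true awareness 90 %**, from the binomial tail P(X ≥ r):

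| n | Interval | r | P(X ≥ r) |
|---|---|---|---|
| 35 | Wald | 32 | 0.531 |
| 35 | Exact or Wilson | 33 | 0.306 |
| 55 | Wald | 49 | 0.690 |
| 55 | Exact or Wilson | 50 | 0.524 |

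If true awareness is 95 %, the exact interval at n = 55 reaches the aim with probability P(X ≥ 50) = 0.944.

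**5. Precision at 55.** At an observed proportion of 90 % (49.5/55, interpolating between counts), the exact 95 % interval runs from 78.9 % to 96.4 %. The lower arm is 11.1 points (90 − 78.9). The Wald half-width is smaller: 1.96 × √(0.09 / 55) = 7.9 points.

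**6. The effectiveness rule of section 9.7.** P(X ≥ 44 of 55) is 0.993 at true awareness 90 % and 0.580 at true awareness 80 %. At exactly 44/55 the lower 95 % limit is 67.0 % (exact) or 69.4 % (Wald). The rule can therefore be met with a lower limit well below 80 %.

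**7. For orientation only.** The protocol sets no target probability. If 80 % were assumed with the exact interval at true 90 %, the probability first reaches the target at n = 107, dips below it again (0.772 at n = 112), and stays above it from n = 113 (checked up to 259). With Wald the sustained size is 86.

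**The case against.** The strongest reply is that 35 is not a mistake. All inputs are disclosed, the formula is a standard precision calculation, and such a calculation gives roughly even odds by construction. The study is descriptive, tests no hypothesis and promises no power. This stands as far as the arithmetic goes: there is no numerical slip, and a descriptive survey need not have a power target. It does not rescue the sentence, because the protocol chose to describe 35 as the size that obtains a lower limit above 80 %, and it is not.

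A second reply is that the figures depend on an interval the protocol does not name, a choice that can be left to the analysis plan. That is fair, so both results are given. The conclusion does not turn on it: even plain Wald, the most favourable, gives only 69 % at 55.

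Two stronger readings are tempting and are not supported:

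- A reader might infer that the study has about even odds of success at 90 % awareness. It does not. Section 9.7 decides on the point estimate, and 44 of 55 is reached with probability 99 % in that case.
- A reader might infer that the study could stop at 35 if recruitment is slow. Nothing allows this. Section 9.1 commits to 55 responses, and section 9.5 answers slow recruitment by adding countries.

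Finally, section 9.2 describes a convenience sample, so any binomial probability is a guide to sampling variation only and takes no account of selection. That caveat applies equally to the interval calculation in the protocol.

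**Conclusion.** The point holds as a misdescription of what the sample size delivers. Sections 4.8 and 9.5 give 35 a property it lacks, and the comparison with 35 therefore lends the planned 55 more reassurance than it earns. At the protocol's own assumption of 90 % awareness, the lower 95 % limit would fail to exceed 80 % in 31 % (Wald) to 48 % (exact or Wilson) of surveys of 55, and in 47 % to 69 % of surveys of 35.

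The chance of declaring effectiveness is unaffected, since the lower limit plays no part in that decision. What is affected is consistency and interpretation: section 9.5 sizes the study on a lower limit above 80 %, while section 9.7 decides on a point estimate of 80 %, which at the threshold has an exact lower limit of 67.0 %. The results assume independent binomial responses and true awareness of 90 %, except where 80 % or 95 % is stated. The number of respondents does not need to change.

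**What to change.** Keep 55. In sections 4.8 and 9.5:

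- Remove 35 as the size that obtains a lower limit above 80 %, or describe it only as the size giving a Wald half-width of 0.1 at an expected 90 %.
- State what 55 delivers, for example: *With 55 respondents and an observed proportion near 90 %, the exact 95 % CI is about 79 % to 96 %. If true awareness is 90 %, the exact lower limit exceeds 80 % (50 or more aware) with probability about 52 %; if true awareness is 95 %, with probability about 94 %.* If another interval is to be used in the analysis, quote the figures for that one (for plain Wald at true 90 %: 49 or more aware, 69 %). The 8-point Wald half-width should not be paired with the exact interval, whose lower arm is about 11 points.
- Add that the effectiveness criterion in section 9.7 is the point estimate and does not require the lower limit to exceed 80 %.

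The cost is wording in two sections. The stated justification becomes less favourable; no respondents are added and the decision rule stays as it is.

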## 9.6 Data management

Questionnaires will be completed on-line and data will be stored on a secure server. Participants must log in using a unique login identification. Every effort will be made to protect participant confidentiality. Participant identifiers will not be disseminated or placed on any reports from this study. Analyses will be conducted with anonymized data. Unless authorized by the participant (for example, in the case of adverse event [AE] or product complaint reporting), only anonymized data will be made available to Medtronic BioPharma in accordance with privacy protection rules as dictated by applicable regulations.

The survey will be conducted using Lighthouse Studio version 9.8.0 or higher from Sawtooth Software. The statistical software used will be SAS version 9.4 or higher.

## 9.7 Data analysis

The study population will include all physicians who are screened, are eligible for this study, and completed the questionnaire. All statistical summaries in this study will be descriptive. Frequencies and percentages, with 95 % confidence intervals (CIs) where appropriate, will be presented. Country specific data will be presented. Additional exploratory analyses and sensitivity analyses may be conducted to identify difference between groups of responders.

The primary analysis is aimed at evaluating the proportion of physicians that is aware of the risk of heterotopic ossification and measures described in the educational materials to minimize that risk. A respondent is considered to be aware if they answer 75 % of the questions with regards to heterotopic ossification and the applicable minimization measures correctly. In the questionnaire there are 12 (sub)questions raised on the occurrence of heterotopic ossification and the related risk minimization measures. Hence a surgeon needs to answer 9 of these correct to be considered aware. In Annex 3 the (sub)questions included in the scoring of awareness are marked. The aRMM will be considered effective if 80 % of the respondents are aware of the described risk of heterotopic ossification and the appropriate measures to minimize them. With the targeted 55 respondents, this means 44 or more need to be aware.

The secondary analysis is aimed at identifying the source of physician knowledge. Based on the received data it will be determined to what extent the educational materials are used and are considered an important source of information for the respondents.

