## 9.8 Quality control

A pre-test of the questionnaire will be performed to ensure its comprehensibility and consistency (see section 9.4).

Suazio will follow its procedures for quality control during the conduct of the survey, which includes but is not limited to:

- Randomization of answer options
- Consistency checks for plausible data
- Checks for completeness of data and perform follow-up as needed

Medtronic BioPharma will follow Medtronic BioPharma procedures and study specific plans will be followed for quality control, which includes but is not limited to:

- Documenting all statistical analysis programs used, including version number
- Archiving the original database and any derived data sets, and all relevant study documents in an electronic document system

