	9.2.1 Exposure? (e.g. date of dispensing, drug quantity, dose, number of days of supply prescription, daily dosage, prescriber)				
	9.2.2 Outcomes? (e.g. date of occurrence, multiple event, severity measures related to event)			$\boxtimes$	
	9.2.3 Covariates and other characteristics? (e.g. age, sex, clinical and drug use history, comorbidity, co-medications, lifestyle)	$\boxtimes$			9.3
9.3	Is a coding system described for:				
	9.3.1 Exposure? (e.g. WHO Drug Dictionary, Anatomical Therapeutic Chemical (ATC) Classification System)				
	9.3.2 Outcomes? (e.g. International Classification of Diseases (ICD), Medical Dictionary for Regulatory Activities (MedDRA))			$\boxtimes$	
	9.3.3 Covariates and other characteristics?		$\boxtimes$		
9.4	Is a linkage method between data sources described? (e.g. based on a unique identifier or other)		$\boxtimes$		
Comments:					
There is no coding planned for covariates and other characteristics, nor is there a linkage foreseen between different data sources.			is there a		
Sect	ion 10· Analysis nlan	Ves	Nο	NI/	Section

Section 10: Analysis plan		No	N/ A	Section Number
10.1 Are the statistical methods and the reason for their choice described?				9.7
10.2 Is study size and/or statistical precision estimated?				9.5
10.3 Are descriptive analyses included?	$\boxtimes$			9.7
10.4 Are stratified analyses included?		$\boxtimes$		
10.5 Does the plan describe methods for analytic control of confounding?			$\boxtimes$	
10.6 Does the plan describe methods for analytic control of outcome misclassification?			$\boxtimes$	

				pago 20 01 00	
Section 10: Analysis plan	Yes	No	N/ A	Section Number	
10.7 Does the plan describe methods for handling missing data?			$\boxtimes$		
10.8 Are relevant sensitivity analyses described?	$\square$			9.7	
Comments:					
There are no confounders (see above) or outcomes measured in this study.					
As the study population will only include completed description needed for the handling of missing data	-	nnaire	es ther	e is no	
Section 11: Data management and quality control	Yes	No	N/ A	Section Number	
11.1 Does the protocol provide information on				Hamber	
data storage? (e.g. software and IT environment, database maintenance and anti-fraud protection, archiving)				9.6	
11.2 Are methods of quality assurance described?	$\boxtimes$			9.8	
11.3 Is there a system in place for independent review of study results?		$\boxtimes$			
Comments:	l .	I			

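### Completers-only analysis set: surgeons who stop during the knowledge test disappear from the awareness proportion, and the plan has no means to detect or bound the bias this could cause

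*Protocol*

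**What the plan says.** Section 9.7 (repeated in abstract section 4.9) defines the analysis set: "The study population will include all physicians who are screened, are eligible for this study, and completed the questionnaire". In Annex 2, checklist item 10.7 on missing data is marked not applicable. The comment under that section, which opens "As the study population will only include completed", gives the restriction to finished questionnaires as the reason.

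The success rule has two levels. For the respondent, 12 (sub)questions are scored: "Hence a surgeon needs to answer 9 of these correct to be considered aware". For the study: "The aRMM will be considered effective if 80 % of the respondents are aware", and "With the targeted 55 respondents, this means 44 or more need to be aware". The rule uses the observed proportion, with no confidence limit.

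In Annex 3 the questions on practice, experience and information sources come first. The adverse-reaction, true/false and surgical-technique items come last, and the scored (sub)questions lie among these.

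Three other provisions bear on the point:
- Section 9.8 lists "Checks for completeness of data and perform follow-up as needed".
- Section 9.2 provides reminders by email, with a telephone call at the second.
- Section 9.7 allows sensitivity analyses, but as an option and only to compare groups of responders.

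Section 9.10 discusses non-response, social desirability, non-random sampling and self-selection. It does not mention stopping part-way.

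**The concern.** Restricting the set to completers does not make missing data irrelevant; it puts the missingness into the definition of the population. A surgeon who logs in, meets the test and stops is eligible and has begun to be measured, but is not counted. As printed, several experience questions offer a don't-know or don't-remember answer and the knowledge questions do not, so a surgeon who does not know must guess or stop. The target is 55 completed surveys, so recruitment can replace each break-off with a completer, and no report of the number is required.

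What is at stake is the effectiveness verdict. If stopping is related to lack of knowledge, the completers' proportion overstates awareness among surgeons who began the test. Section 9.10 already concedes that selective participation can inflate awareness. Break-off is a second selection step that could act in the same direction, and it is neither listed nor examined.

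**Working it through.** **Inputs.** From section 9.5: "an alfa of 0.05 with a two-sided interval and a distance from proportion to limit of 0.1", which "was used with the expected proportion of 90" %; minimum size 35; target 55 completed surveys. From section 9.7: 9 of 12 for the respondent, 80 % and 44 of 55 for the study. No break-off rate is given. Section 9.5 states a response rate of about 60 % but does not separate surgeons who never start from those who stop. The break-off numbers and rates below are therefore assumptions.

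**The plan's own figures.** n = 1.96² × 0.90 × 0.10 / 0.10² = 34.57, rounded up to 35. 0.75 × 12 = 9. 0.80 × 55 = 44. All three reproduce.

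**Break-offs counted as not aware.** With x aware among 55 completers and k break-offs, the proportion is x/(55 + k). The number of aware completers needed is 0.80 × (55 + k), rounded up.

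| k (assumed) | x = 44 | x = 50 | aware completers needed |
|---|---|---|---|
| 0 | 80.0 % | 90.9 % | 44 |
| 1 | 78.6 % | 89.3 % | 45 |
| 3 | 75.9 % | 86.2 % | 47 |
| 5 | 73.3 % | 83.3 % | 48 |
| 7 | 71.0 % | 80.6 % | 50 |
| 8 | 69.8 % | 79.4 % | 51 |

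The expected 90 % corresponds to 0.90 × 55 = 49.5, so x = 50 represents the planning case. The verdict holds while k ≤ x/0.80 − 55. This gives k = 0 at x = 44, 2 at x = 46, 5 at x = 48 and 7 at x = 50.

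**The opposite extreme.** If every break-off were aware, the proportion would be (x + k)/(55 + k). With x = 44 and k = 5 this is 49/60 = 81.7 %, against 44/60 = 73.3 % in the worst case.

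**Differential break-off.** Let p be the true awareness among starters, and a and u the break-off rates of aware and unaware surgeons. Awareness among completers is p(1 − a) / [p(1 − a) + (1 − p)(1 − u)]. The pass probability is the binomial chance of at least 44 aware among 55 completers. For p = 0.75:

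| a | u | awareness among completers | chance of passing |
|---|---|---|---|
| equal | equal | 0.750 | 0.25 |
| 5 % | 20 % | 0.7125/0.9125 = 0.781 | 0.44 |
| 5 % | 30 % | 0.7125/0.8875 = 0.803 | 0.60 |
| 15 % | 5 % | 0.6375/0.8750 = 0.729 | 0.15 |

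The denominators are the fractions of starters who finish. The 5 % v 20 % case therefore implies 55/0.9125 ≈ 60 starters, or about 5 break-offs, and the 5 % v 30 % case 55/0.8875 ≈ 62 starters, or about 7. Both lie within the range of the first table.

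**The case against.** A reader might infer that the completers-only set does push awareness upwards and so favours an effective verdict. The documents do not support that. They give no break-off rate and no statement that unaware surgeons stop more often; equal break-off leaves the estimate unbiased and the reverse pattern lowers it.

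The mechanism can also be doubted. The knowledge items are almost all closed questions, so a surgeon who does not know can guess and finish. The survey is described as short, compensation is offered, and the payment message appears at the end. Together with reminders and completeness checks, these features work against stopping late. They may make break-off rare, but they do not show how often it happened or to whom.

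A reader might also infer that one break-off overturns the result. That is true only at exactly 44 of 55. One additional unaware completer would do the same, so the absence of margin belongs to the point-estimate rule, not to the analysis set.

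Nor does section 9.8 say that scored answers are reopened or prompted during follow-up. It only fails to exclude this, which is a reason to clarify the text and not evidence of contaminated answers.

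Finally, counting unanswered items as not correct has its own downward bias, because a surgeon interrupted while answering well may be scored unaware. That objection stands against making it the primary analysis. It does not stand against using it as a bound.

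**Conclusion.** The point holds in a conditional form. The protocol itself fixes a completers-only set and uses that choice to close the missing-data question, so this is not a detail left to an analysis plan. As written, the study can neither detect break-off during the test nor bound its effect. An upward bias is possible, but neither its presence nor its size can be established from the documents.

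The consequence depends on where the result falls. Near 44 of 55, one to five break-offs counted as not aware give 78.6 % to 73.3 %. Near the expected 90 %, it takes eight to change the conclusion. Under the assumed 5 % v 20 % and 5 % v 30 % break-off rates and a true awareness of 75 %, the chance of passing rises from 0.25 to 0.44 and 0.60. These are illustrations, not estimates. The change is a modest and cheap improvement, and the case does not justify replacing the primary analysis set.

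**What to change.** - Keep the completers-only proportion as the primary result.
- In section 9.7, require the report to give the number of eligible surgeons who opened the first scored (sub)question and did not finish, by country and by last item reached.
- Add one pre-specified sensitivity analysis over all eligible surgeons who opened that item, with unanswered scored items counted as not correct. For the tick-all questions, treat an item never reached as unanswered, so that blank boxes do not earn credit.
- State that the effectiveness conclusion will be qualified if the two proportions fall on opposite sides of 80 %.
- Amend checklist item 10.7 to refer to this analysis.
- State in section 9.8 that scored items are not completed through follow-up prompts.

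Section 9.6 says that data are stored on a secure server but not that unfinished questionnaires are retained, so the sponsor should confirm that the survey platform keeps partial responses. Surgeons who withdraw consent under section 10 should be excluded from the sensitivity analysis.

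The cost is a few sentences and one extra table, provided partial responses are kept. The downside is small: some surgeons will stop for lack of time, so the sensitivity figure should be labelled a lower bound on awareness among those who began the test.
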